## **SUMMARY**

### **Background**

In recent years, Western populations have experienced an increase in life expectancy and therefore an ageing population. This has led to an increase in the number of low-energy hip fractures, which have a major impact in terms of mortality, mobility and loss of function in activities of daily living in this segment of the population.

### **Objectives**

To determine the impact in terms of functional recovery, return to pre-hip fracture functional status, of elderly patients treated with the new multimodal therapeutic exercise programme and follow-up for one year compared to patients treated with the previously developed standardised nursing care plan at the Hospital San Juan de Dios de León.

### **Methodology**

Observational study of ambispective cohort with two groups, an exposed cohort (retrospective) and a non-exposed cohort (protective factor), made up of people over 65 years of age referred from the Emergency Department of the University Care Centre of León (CAULE) with a confirmed diagnosis of hip fracture, who underwent hip fracture surgery in the Hospital San Juan de Dios de León during the years 2020 and 2021.

In order to carry out an analysis of the new care model proposed by the area of orthogeriatrics for the year 2021: functional recovery programme and its follow-up through a digital application, the entire simple universe will be included (analysis of the complete cohort) with follow-up over a period of one year.

### **Keywords (maximum 5)**

*Hip fractures, Physiotherapy, Functional capacity, Frail elderly,*

## BACKGROUND AND CURRENT STATUS OF THE ISSUE

### **Introduction.**

Spain is one of the countries with the highest life expectancy at birth in the world, with a life expectancy of 80.0 years for men and 85.6 years for women in 2015 (1). This has led to a considerable increase in the population of elderly people over the last century (2).

This increase does not imply that this high life expectancy is accompanied by years of good health, as older people may suffer from diseases and health problems that lead to a loss of quality of life, without resulting in immediate death (3-5).

One of the most important problems associated with ageing is hip fractures, as it generates a significant impact in terms of morbidity, mortality and functional deterioration. In Spain, this problem causes an incidence of 103 cases per 100,000 inhabitants, with the rate increasing from the age of 75 onwards to 2,534 per 100,000 inhabitants (6.7).

Hip fractures have a very important impact on older people, since in addition to their functional impact on gait, they have an associated inability to perform other activities of daily living and a cognitive impact (8).

Following hip fractures, these patients require many modifications to their daily lives, ranging from increased assistance at home to the need for residential care. This leads to increased health care costs, not only during the hospital stay, but also after discharge (9).

Different clinical practice guidelines have been published in recent years with recommendations aimed at reaching a consensus and improving the care of patients with this pathology (10-13). Despite these recommendations, their implementation in Spanish hospitals has been irregular, generating great variability in the care provided in this process. This has led to differences in patient care depending on the hospital where the patient has been treated, such as: delays in the performance of surgeries, an increase in the number of days of hospitalisation, differences in the number of rehabilitation sessions and differences in the number of consultations (14,15).

What does seem clear is that every elderly person who suffers a hip fracture should undergo a comprehensive assessment including: the cause of the fall, assessment of comorbidity and clinical stability, previous medications, pain, nutritional and hydration status, continence, and cognitive, functional and social status (11).

According to clinical practice guidelines, rehabilitation should begin from the moment of admission, following a multidisciplinary approach, where all those involved are aware of the treatment plan and reasonable expectations of recovery (10-13,16). Early mobilisation, weight bearing and active recovery are the basis of rehabilitation treatment, resulting in lower mortality six months after the intervention and better ambulation (17).

It is estimated that 60-80% of elderly people with hip fractures were walking independently before the fracture. One of the most important goals is to achieve the same degree of ambulation as before the fracture. For this reason, it is important to use validated scales that can provide information on the patient's previous state and help to assess whether or not the objectives have been achieved. Despite this, only 50% manage to recover their pre-fracture state (10).

To achieve this goal, it is desirable that the patient be operated on as soon as possible and begin sitting up the day after surgery, thus facilitating early loading as soon as possible, provided that drains or other devices permit (10,11).

Specific rehabilitation treatment will aim to increase joint mobility; strengthening of the gluteal and quadriceps muscles; re-education of walking as soon as possible, first with the use of devices and progressively more and more independently (10).

In recent years, several reviews have studied the implementation of different rehabilitation programmes for the elderly after hip fracture, with the aim of increasing physical and psychosocial function (18-23).

Several of these reviews (18,19,21) have focused on comparing multidisciplinary rehabilitation with routine orthopaedic care after hip fracture. These studies found that multidisciplinary rehabilitation was associated with a modest but significant reduction in adverse outcomes such as death. These results were confirmed by Wang et al. (22) who found significant differences in terms of reduced mortality during hospitalisation or during subsequent follow-up.

While rapid surgery, early mobilisation and a multidisciplinary team-based approach to rehabilitation seem important for restoring the patient's previous function, there are discrepancies about the contribution of various components of this intensive approach to interventions specifically focused on improving independence such as dressing, shopping and interacting in the community (18,21,24).

Handoll et al. (20) in their review analysed different strategies focused on functional recovery of the elderly after hip fracture surgery, both in and out of the hospital setting.

Their findings highlight the lack of evidence to determine the most effective strategy to help people continue walking after surgery.

On the other hand, Handoll et al. (19) in another review, analysed the difference in costs between patients treated with a multidisciplinary rehabilitation team and regular orthopaedic care, being unable to establish which of the two interventions is more beneficial from an economic point of view. The study includes some recommendations suggesting the inclusion of direct and indirect cost evaluation including both economic and social criteria such as the burden on caregivers. These results contrast with those found by Sabharwal et al (23), who found that orthogeriatric care models in the treatment of frail patients with hip fractures demonstrate a reduction in mortality and morbidity rates, with a better cost-effectiveness of treatment.

Social and psychological factors such as fear of falling, self-efficacy, perceived control and coping strategies are considered important in hip fracture recovery. Positive affect" (e.g. optimistic outlook) appears to be an important predictor of recovery in activities of daily living in various clinical groups and has been associated with a significant reduction in the risk of frailty (25). Mastery or internal control has been shown to be associated with improved coping, adjustment and general mental health after hip fracture. However, strategies such as reorientation, cognitive behavioural therapy and intensive occupational therapy did not show changes in psychosocial outcomes, function and quality of life. This suggests that the transition between acute care, rehabilitation and community care requires further attention. Crotty et al. (18) who did address these social and psychological factors in their review, were unable to establish clear criteria for recommendation in practice because the design and sample size of the included studies were inadequate to draw clear and conclusive conclusions.

It appears that the concept of multidisciplinary treatment is not without certain limitations (26). This type of treatment has been implemented heterogeneously, which makes it difficult to interpret the results obtained and, therefore, to determine best practice (22,23).

Research has addressed the study of different functional parameters with multiple results, however, the aspect of patient participation has been less studied despite being described as the most important outcome for people with disabilities, their families and society (27). Encouraging patients to take an active role has been shown to lead to greater motivation and better outcomes. However, the way in which care after hip fracture is structured, despite the many benefits that can be found, has been described as a possible limiting factor for patient participation because staff are focused on the care of the patient and often do not focus on identifying the personal needs of patients (26).

Based on all of the above, the comprehensive treatment of patients with a hip fracture does not only include the surgical aspect, but is much more complex. It should aim to reduce mortality and recover the functional and psychosocial situation prior to the fracture, trying to achieve these objectives in the shortest possible time and at the lowest possible cost.

### **Justification of the Study**

In recent years there has been an increase in the number of hip fractures and this is expected to continue until 2050. From 1.26 million in 1990 to 21.3 million in 2050 (28). Given the ageing of Western populations, the total number of hip fracture cases and their economic consequences are likely to increase considerably. This, coupled with the negative outcome for survivors, many of whom end up being more dependent than before the fracture, calls for studies that address the effectiveness of a functional recovery programme that addresses both the physical and psychosocial spheres of the patient, both in and out of hospital.

The target population of this study is an ageing population, living in a rural environment, far from relatives or people who can help them with daily tasks and with difficulties in accessing the different resources to achieve an optimal recovery. These people therefore need a level of functional recovery that can give them back the level of independence they had before the hip fracture.

## HYPOTHESES AND OBJECTIVES

### Overall objective

- To determine the impact in terms of functional recovery, return to pre-hip fracture functional status, of elderly patients treated with the new multimodal therapeutic exercise programme and follow-up for one year compared to patients treated with the previously developed standardised nursing care plan at the Hospital San Juan de Dios de León.

### Specific objectives

- To describe the improvement in gait ability in patients undergoing hip surgery after a functional recovery programme compared to the historical control group (exposed cohort).
- To describe the clinical and functional characteristics of the patients operated on for hip fracture in the SJD hospital in León who are being followed up by the new system of care implemented in comparison with the historical control group (exposed cohort).
- To analyse risk and protective factors related to the level of dependency and mortality at 30 days and one year of follow-up in patients operated on for hip fracture at the SJD hospital in León.
- To describe the impact of a functional recovery programme on the prevention and treatment of sarcopenia in the new unexposed cohort.
- To describe the quality of life and patient-reported outcomes in the new unexposed cohort.
- To analyse the impact of a functional recovery programme on the prevention of falls in elderly patients who have undergone hip fracture surgery.

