## METHODOLOGY

### Study design

Longitudinal analytical observational study of ambispective cohorts with two groups, an exposed cohort (retrospective) and a non-exposed cohort (protective factor), made up of people over 65 years of age referred from the Emergency Department of the University Care Centre of León (CAULE) to the Hospital San Juan de Dios de León (HSJD) with a confirmed diagnosis of hip fracture and who underwent hip fracture surgery in the latter during the years 2020 and 2021, and who will be followed up during the year after surgery, in the latter, to undergo hip fracture surgery during the years 2020 and 2021 and who will be followed up during the year following the surgery.

Two groups:

- Non-exposed cohort (protective factor): group of patients operated on during the year 2021 in HSJD for hip fracture and to which the new programme implementing functional recovery and therapeutic exercise will be applied with follow-up for one year. The implementation of a functional recovery plan and subsequent follow-up is considered a protective factor in relation to the loss of functionality.
- Exposed cohort (retrospective): complete cohort of patients operated on during the year 2020 in HSJD for hip fracture and to whom no specific functional recovery plan was applied.

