## Sampling

**Sample and procedure for inclusion of patients in the unexposed cohort.**

In order to carry out an analysis of the new care model (functional recovery programme and patient follow-up through a digital application), the entire simple universe will be included, a complete cohort analysis, with follow-up at 1, 3, 6 and 12 months using a digital toolFollow-up will be carried out at 6 weeks, 4 months and 12 after discharge according to the protocol of the orthogeriatrics unit.

The patient will be given instructions on how to download the application to their mobile device. The application is available in the open repository of mobile applications for public use. Once the app is installed, the patient will be provided with a personal access code that does not include recognisable personal data. This code will be used to connect to the therapeutic plan and to the questionnaires provided by the patient when registering with the Traumatology Service. Only the principal investigator (PI) will have a system of correlation between the code and the patient's personal data, be responsible for its safekeeping.

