#### **Variables**

In the two groups that form part of this study, different variables specified in the database adapted from the National Hip Registry and the *International Fragility Fracture Network*, of which the HSJD is a member, will be collected.

Until now, data collection and patient follow-up was completed after one month and the data was transferred annually to the National Hip Fracture Register. In the new model proposed by orthogeriatrics unit of the HSJD, patients will be followed up in person at one and a half months, four months and one year, and at discharge, one month after discharge, three months, six months and one year, by means of a digital application.

The variables to be collected are described below:

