- Level 2: non-functional ambulation. Walking with great physical assistance from a person, and/or walking is only possible within a therapy session at home, or in hospital, between parallel bars
- Level 3: ambulation in the home, walking with light physical contact with a person. Is able to walk only indoors, on flat, horizontal surfaces, usually within a defined area.
- Level 4: walks autonomously in the home or neighbourhood environment, but needs supervision by a person. They can walk on uneven surfaces and can climb an occasional step.
- Level 5: independent community walking. Can walk on uneven terrain, up and down steps, ramps, kerbs, etc. Can walk considerable distances, but with obvious limp.
- Level 6: walks normally both indoors and outdoors, in the absence of a limp or other abnormality.

This scale is administered at admission, 6 weeks, 4 months and 1 year.

**Second group: the variables collected in this second section form part of the new model of care established by the orthogeriatric service, whereby the hip fracture patient will be followed up for up to one year after the intervention, therefore, they are variables that can only be measured in the cohort of unexposed patients.**

Patient follow-up variables (Table II):

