30-39: Mild to moderate impact.

40-48: Satisfactory condition.

This scale is administered at 1, 3, 6 and 12 months.

- **Monitoring of adverse events.**

During the follow-up period, information will be collected on variables derived from post-surgical and medical complications, and falls risk monitoring will be performed.

- **Adverse events. Catalogued in:**

0= Fall.

- 1= Pneumonia.
- 2= New fractures.
- 3= Dementia.
- 4= Acute Myocardial Infarction.
- 5= Pulmonary embolism.
- 6=Deep vein thrombosis.
- 7= Death.

This scale is administered at 6 weeks, 4 months and 1 year.

- **Falls risk scale: STRATIFY scale.**

It can predict which patients are at high risk of falls, with sensitivity values of 92% and specificity of 68% for the elderly population (46).

The total score of the STRATIFY scale is obtained based on the sum of the answers to the five questions, which can take values between zero and five. A score of 0 corresponds to a risk considered low, equal to 1 corresponds to a moderate risk and, finally, greater than or equal to 2 corresponds to a high risk (47).

Question:

1. Patient hospitalised for falls or with episodes of falls during hospitalisation?
2. Restless patient?
3. Are you a patient with visual impairment that affects your daily activity?
4. Patient with a frequent need to use the toilet?
5. Does the patient have a transfer or mobility score of 3 or 4?

However, in the last question, the score is obtained by combining two answers from the modified Barthel index in relation to, respectively, the patient's ability to:

- Transferring from bed to a chair
  - 0: incapable.
  - 1: needs significant assistance.
  - 2: Needs minimal assistance.

3: Independent.

- Level of mobility of the patient:

0: Immobile.

1: Independent with the help of a wheelchair.

2: Use walking aids or walk with the help of a person.

3: Independent.

This scale is administered at 6 weeks, 4 months and 1 year.

- **Quality of life analysis: EQ-5D-5L questionnaire (ANNEX IV) (48).**

It is a self-administered questionnaire divided into two parts, the descriptive system and the Visual Analogue Scale (VAS).

- The descriptive system EQ-5D-5L. describes health status along five dimensions:
  - Mobility.
  - Self-care.
  - Daily activities.
  - Pain/discomfort.
  - Anxiety/depression.

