**Table III. Summary of variables, assessment instruments and collection period**

Variable	Questionnaire	Time of administration
March Capacity	RNFC scale	Entry, at 6 weeks, 4 months and 1 year.
	The walking capacity assessment scale (mFAC).	Entry, at 6 weeks, 4 months and 1 year.
Physical capacity	Barthel Index	At 6 weeks, 4 months and 1 year.
	Oxford Hip Score Scale	At the 1st, 3rd, 6th and 12th month.
Sarcopenia	SARC-F Scale	At 6 weeks, 4 months and 1 year.
Adverse Events	STRATIFY scale	At 6 weeks, 4 months and 1 year.
	Medical complications (ad hoc questionnaires)	At 6 weeks, 4 months and 1 year.
Quality of life	Questionnaire EQ-5D-5L	At the 1st, 3rd, 6th and 12th month.

- The functional recovery programme designed and implemented as standard practice from 1 January 2021. This programme consists of a series of presentations and videos, in simple language with information and recommendations. It will provide answers to patients' most frequently asked questions and will also allow patients to receive reminders regarding their care (recommended exercises, precautions to take in certain circumstances, alerts, etc.).

It is the clinician and the patient, or family member if applicable, who enters the data directly into the application, prior to accepting the legal clauses to that effect.

The study variables collected in the project are included among the clinical variables included in the orthogeriatric protocol for the care of hip fracture patients at the HSJD. In order to analyse those established for this study, the variables will be extracted from the data collection platform, the PI being responsible for the storage and processing of the data in accordance with current legislation.

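### With the data listed, 30-day and one-year mortality cannot be obtained on the same basis in the 2020 and 2021 cohorts

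*Combined protocol and SAP*

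**What the plan says.** The Specific objectives include "To analyse risk and protective factors related to the level of dependency and mortality at 30 days and one year of follow-up". The population is everyone who had hip fracture surgery at the hospital. Neighbouring objectives on sarcopenia and quality of life name the 2021 cohort; this one names no cohort.

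Death appears as a study variable in one place: category 7 of medical complications (Table II, continuation, repeated under Monitoring of adverse events). For timing, the text there says "This scale is administered at 6 weeks, 4 months and 1 year". Table III gives the same three times for "Medical complications (ad hoc questionnaires"). No date of death is listed. The item belongs to the second group of variables, of which the protocol says "they are variables that can only be measured in the cohort of unexposed patients", meaning the patients operated on in 2021.

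Two time origins are used. Under Sampling, follow-up visits "will be carried out at 6 weeks, 4 months and 12 after discharge". Study design describes patients "who will be followed up during the year after surgery".

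For the care model before 2021, the Variables section says "data collection and patient follow-up was completed after one month", after which data went to the national registry. The 2020 data are to come from that registry reporting system.

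The withdrawal criteria for the 2021 cohort include death by hospital discharge, the occurrence of complications, and non-compliance with the plan or the assessments. No withdrawal criteria are given for the 2020 cohort.

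**The concern.** The objective fixes two time points, 30 days and one year, and no listed variable is measured at the first of them. A death code collected at a 6-week visit shows that a patient died before the visit, not whether the death came before day 30. The item is also confined to one cohort, while the objective and the Study design section cover patients from both years.

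Anyone who computes mortality from the listed items would have to use the 6-week code as a stand-in for 30 days in 2021, set beside a 2020 figure that stops at about one month. At one year there would be nothing listed to set beside the 2021 figure. The withdrawal rule adds a second asymmetry: patients who die in hospital, or who have a complication (death is itself coded as one), could leave the 2021 cohort, while their 2020 counterparts stay in.

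**Working it through.** The plan states no mortality rate, event count or power for this objective, so there is no figure to reproduce. The check is date arithmetic followed by a cross-read by cohort and time point.

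**Inputs.** Target: 30 days (Specific objectives). First death code: 6 weeks = 42 days (Monitoring of adverse events, Table III), counted from discharge (Sampling). Last death code: 12 months, taken as 365 days, from discharge. Length of stay *L*: not given in the documents, so assumed at 0 to 15 days.

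**Formulas.** Day of first code after surgery = 42 + *L*. Days beyond the target = 42 + *L* − 30. If the code counts every death since surgery and the hazard is constant over the window, the share of those deaths within 30 days = 30 / (42 + *L*). Overrun of the one-year visit = *L* / 365.

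| Assumed stay *L* (days) | First code, day after surgery | Days beyond day 30 | Share of deaths within 30 days | Share after day 30 | One-year visit, day after surgery | Overrun |
|---|---|---|---|---|---|---|
| 0 | 42 | 12 | 30/42 = 71% | 29% | 365 | 0.0% |
| 5 | 47 | 17 | 30/47 = 64% | 36% | 370 | 1.4% |
| 10 | 52 | 22 | 30/52 = 58% | 42% | 375 | 2.7% |
| 15 | 57 | 27 | 30/57 = 53% | 47% | 380 | 4.1% |

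The days in columns two and three follow from the schedule and *L* alone. The shares also need the constant hazard. If deaths are concentrated soon after surgery, the share after day 30 is smaller, but the code still cannot separate the two periods.

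**Cross-read.**

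| | 30 days | One year |
|---|---|---|
| 2021 cohort | Not derivable from the listed items: the first code is at day 42 + *L* | Approximately derivable from the codes accumulated by the one-year visit, which overruns by *L* days |
| 2020 cohort | Not listed, but possibly in the registry extract, since follow-up reached one month | No stated source |

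The app contact one month after discharge does not fill the upper left cell. Table III assigns only the Oxford Hip Score and the EQ-5D-5L to the app time points.

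**Direction of bias.** If the 6-week code is used as 30-day mortality in 2021, the longer window adds deaths to that cohort. If in-hospital deaths are withdrawn in 2021 and kept in 2020, deaths are removed from the same cohort. The two effects oppose each other, and the documents give nothing from which to size either.

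**The case against.** The strongest reply is that a reader might infer that neither mortality figure can be derived at all, and the documents do not support that. The 2021 cohort has a one-year contact at which death is coded, and on the assumed stays the discharge clock shifts it by no more than about 4%. The 2020 follow-up ran to one month, close to the 30-day point. This part of the reply stands.

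The absence of vital status from Table I also proves little. That table covers characteristics before surgery, so death would not be expected in it. It is introduced as a list of what the variables include, and the first group is defined by a registry protocol that is not reproduced. What the 2020 extract holds is unknown, not shown to be absent. Likewise, the ad hoc complication questionnaires are not in the annexes; one can say that no date of death is listed, not that none will be recorded. Caregivers, relatives and clinicians can enter data, so a death could be reported without the patient.

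Finally, the objective asks for risk and protective factors and names no comparison with the historical group. The hypothesis concerns function, and the programme is called protective against loss of functionality. A reader might infer that a promised test of the programme on mortality is impossible, but the plan does not explicitly promise that test. Factors such as age or prior mobility could be studied within 2021 alone.

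The reply leaves two cells of the cross-read empty. Even an analysis confined to 2021 lacks a 30-day outcome, and the objective as worded still includes the 2020 patients at one year. It also leaves the one-sided withdrawal rule untouched.

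**Conclusion.** The point holds in limited form. With the listed data the mortality objective cannot be met on the same basis in both cohorts: 30-day mortality in 2021 is not derivable, and one-year mortality in 2020 has no stated source. The 30-day gap does not depend on any assumption about stay, because the first code comes at least 12 days too late even with a stay of zero. For assumed stays of 5 to 15 days it comes 17 to 27 days late, and at a constant hazard 36% to 47% of the deaths it carries would fall after day 30. Those percentages are illustrative, resting on an assumed stay, a constant hazard and a code that counts all deaths since surgery.

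A reader might also infer that the programme would look worse, because its window is longer, or better, because early deaths are withdrawn. The documents support neither; the net direction is unknown. Mortality is part of one specific objective and not the main functional outcome. Even so, following the schedule and the withdrawal rule as written would give a wrong or missing figure for a named outcome, so it should be corrected before analysis.

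**What to change.** - For every eligible operated patient in both years, record the date of surgery and the date of death, or the date last known alive, from the same hospital or health-service record.
- Define mortality as death within 30 and within 365 days of surgery, and use that time origin throughout the mortality analysis.
- Count in-hospital deaths and deaths after withdrawal as deaths in the mortality analysis, in both cohorts.
- List vital status as a variable for both cohorts, instead of only inside the 2021 complications item.
- If one-year vital status cannot be retrieved for 2020, limit the one-year mortality objective to the 2021 cohort and say so.

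The cost is two date fields, one record look-up per patient and a change of protocol wording, with no new visits. The main downside is the time for the retrospective look-up in the 2020 cohort.
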